#### **9.1.3 Safety Follow-up**

Upon permanent discontinuation from the study treatment for any reason (including subjects who complete 12 cycles of treatment), a safety follow-up visit will be performed approximately 30 (+3) days after the last dose of all study drug(s) unless the subject is lost to follow-up, has withdrawn full consent, or has died. Subjects who discontinue treatment due to confirmed PD are also to complete the safety follow-up visit.

#### **9.1.4 Long-term Follow-up**

After discontinuation from study treatment, subjects who do not have confirmed PD are required to continue follow-up every  $28 \pm 7$  days for survival, disease response assessments and reporting of new antimyeloma treatment until 12 months after randomization, first subsequent antimyeloma treatment, death, loss to follow-up, withdrawal of full consent, or confirmed PD, whichever comes first. For applicable study subjects, long-term follow-up will commence 28 days after the Safety Follow-up visit.

All subjects with confirmed PD before 12 months from randomization will be followed for survival every  $28 \pm 7$  days until 12 months after randomization, death, loss to follow-up, or withdrawal of full consent, whichever comes first. For applicable study subjects, long term follow-up will commence 28 days after the Safety Follow-up visit.

Disease response assessments and survival information will be collected as indicated in the Schedule of Activities ([Table 2-1](#)).

#### **9.1.5 End of Study**

The end of study for each subject is the date they withdraw full consent from the study, completes the final safety follow-up visit (following 12 cycles of treatment) or final long-term follow-up visit (whichever is later), or death. This could be a safety follow-up visit 30 (+3) days after last dose of all study drug(s) or a final long-term follow-up response or survival assessment.

## **9.2 Description of General Study Assessments and Procedures**

The sections below provide a description of the individual study procedures for required time points.

### **9.2.1 General Assessments**

#### **9.2.1.1 Informed Consent**

All subjects or their legally authorized representative must sign and personally date the IRB/IEC approved ICF before any study-specific procedures are performed.

#### **9.2.1.2 Demographics**

Demographic data collection including sex, age, race, and ethnicity will be collected to study their possible association with subject safety and treatment effectiveness.

Additionally, demographic data will be used to study the impact on biomarker variability and PK of the protocol-required therapies.

#### **9.2.1.3 Medical History**

The Investigator or designee will collect a complete medical and surgical history that started within 30 days prior to signing of the ICF. In addition, medical history will include collecting information on the subject's significant medical conditions, prior surgeries, and neuropathy history, dating back to the original diagnosis. Record all findings on the medical history eCRF. The current toxicity grade will be collected for each condition that has not resolved. Cardiovascular risk factors, which include family history of cardiovascular disease and smoking history, will also be collected.

In addition to the medical history above, multiple myeloma history must date back to the original diagnosis. For subjects who are being referred to the research site, critical referral information will constitute multiple myeloma information from source notes. Prior lines of multiple myeloma treatment are defined as a planned course of therapy.

Therefore, during initial treatment, the induction  $\pm$  autologous stem cell transplant  $\pm$  consolidation and maintenance would be considered 1 line of therapy (see Section 12.8 for additional guidance on lines of therapy).

#### **9.2.1.4 Physical Examination**

Physical examination will be performed as per standard of care. Physical examination findings should be recorded on the appropriate eCRF (eg, medical history, event).

#### **9.2.1.5 Physical Measurements**

Height (in centimeters) should be measured without shoes. Weight (in kilograms) should be measured without shoes.

Body Surface Area should be calculated using the Mosteller Formula (Mosteller, 1987):

$$\text{BSA (m}^2\text{)} = ([\text{Height(cm)} \times \text{Weight(kg)}]/3600) ^{1/2}.$$

#### **9.2.1.6 Substance Abuse History**

Obtain a detailed history of prior and/or concurrent use of tobacco.

#### **9.2.1.7 Performance Status**

The subject's performance status will be assessed using the ECOG PS (Section [12.9](#)).

### **9.2.2 Efficacy Assessments**

Disease assessments will be based on central laboratory data and local imaging obtained every  $28 \pm 7$  days until confirmed PD (Section [9.2.2.5](#)) irrespective of cycle duration including dose delays and treatment discontinuation.

Disease response and progression assessments include: serum protein electrophoresis (SPEP), urine protein electrophoresis (UPEP), serum-free light chain (SFLC), serum and urine immunofixation (SIFE, UIFE, respectively) (Section [9.2.2.1](#)), bone marrow sample evaluation (Section [9.2.2.2](#)), serum calcium, bone lesion evaluation (Section [9.2.2.3](#)) and plasmacytoma evaluation (Section [9.2.2.4](#)).

#### **9.2.2.1 SPEP, UPEP, SFLC, SIFE, and UIFE**

Serum protein electrophoresis, UPEP, SIFE, UIFE, and SFLC will all be conducted at the central laboratory. Samples will be collected every  $28 \pm 7$  days (starting from cycle 1 day 1) irrespective of cycle duration including dose delays and treatment discontinuation. Blood will be obtained for SFLC, SPEP, and SIFE. Twenty-four-hour urine samples will be obtained for UPEP and UIFE. A 24-hour urine sample obtained as standard of care may be used as the screening assessment, if obtained within 24-hours prior to signing consent and sent to central lab for analysis. Results for SPEP, UPEP, or SFLC must be available at screening and before randomization. Serum protein electrophoresis, UPEP, and SFLC will be repeated on cycle 1 day 1 (unless screening values are within 14 days of cycle 1 day 1).

Post cycle 1 day 1, UPEP and UIFE will be collected every 28 days as part of every myeloma disease assessment, along with SPEP, SIFE, and SFLC, and submitted to the central laboratory for processing.

Subjects will be evaluated for disease response and progression according to the IMWG response criteria in Section 12.11. Disease status categories include sCR, CR, VGPR, PR, SD, and PD. Investigator evaluation of disease response is to be based solely on the central laboratory results, not on local laboratory results for laboratory-based parameters.

The following confirmation assessments are required for all response categories (sCR, CR, VGPR, and PR; refer to definitions in Section 12.11):

- all response categories require 2 consecutive assessments before initiation of any new therapy
- all categories also require no known evidence of progression including new bone lesions if radiographic studies were performed
- confirmation of CR or better requires bone marrow assessment (aspirate or biopsy per IMWG-URC guidelines; sCR determination in this study requires a bone marrow biopsy or aspirate clot for immunohistochemistry)
- extramedullary plasmacytoma evaluation (if present at screening)

#### **9.2.2.2        Bone Marrow Sample Evaluation Including FISH and MRD[-]CR Assessment**

A baseline bone marrow aspirate sample will be collected during the 28-day screening period, or prior to dosing at cycle 1 day 1 and used to confirm the diagnosis and quantify the percent (%) of myeloma cell involvement. Where the screening platelet count is  $< 50 \times 10^9/L$ , the site must allow sufficient time for the bone marrow sample to be processed and the percent (%) myeloma cell involvement reported before randomization.

The priority order of testing of the baseline bone marrow aspirate sample by the central laboratory, based on the volume and quality of sample obtained, will be

- for tumor specific sequence identification for MRD measurement by next-generation sequencing (NGS)
- cytomorphology analysis to confirm multiple myeloma diagnosis and to quantify the percent of myeloma cells in bone marrow
- fluorescent in situ hybridization (FISH).

Sites should also follow this guidance when collecting sample from the subject: if the bone marrow aspirate sample taken at baseline and received by the central lab are found to be of insufficient quantity or quality for testing at least 1 measure above, the site may be contacted to request provision of a suitable archival bone marrow aspirate or core sample to send to the central laboratory for analysis.

After screening, bone marrow samples are required at 2 subsequent time points:

- to confirm a response of CR or better, bone marrow samples should be collected within 35 days of the second consecutive laboratory disease assessment which shows CR. Samples to be collected at CR confirmation are:
  - Cytomorphology to assess percent (%) plasma cells: from a bone marrow aspirate
  - MRD: from a bone marrow aspirate, which should be frozen
  - Immunochemistry to confirm sCR: a bone marrow biopsy (trephine) or an aspirate clot
- At 12 months ( $\pm$  4 weeks) from randomization (fixed landmark analysis), a sample is required for MRD assessment unless MRD analysis was done within the past 4 months, or if the subject has started new anti-myeloma therapy prior to 12-month landmark, or disease progression is recorded.

#### **9.2.2.3        Bone Lesion Assessment (Skeletal Survey, CT, or PET/CT)**

Skeletal survey will include lateral radiograph of the skull, anteroposterior and lateral views of the spine, and anteroposterior views of the pelvis, ribs, femora, and humeri. Low-dose whole body computed tomography or fluorodeoxyglucose-positron emission tomography/computed tomography (FDG-PET/CT) may be used in place of skeletal survey. A standard of care bone lesion radiographic assessment performed within 45 days of Cycle 1 Day 1 may be used as the Screening assessment, and does not need to be repeated, unless standard of care method of assessment is different from as specified above, ie, MRI bone lesion assessment would not be allowed to substitute for the Screening bone lesion assessment.

It should be repeated if worsening clinical symptoms suggest PD or as clinically indicated. The same method of assessment used at baseline will be used throughout the study. These imaging studies will be read locally.

#### **9.2.2.4        Extramedullary Plasmacytoma**

Extramedullary plasmacytoma evaluation will be conducted at screening only if a lesion is suspected clinically. The evaluation may be done within 28 day screening window, if performed as a part of standard of care. If a measurable extramedullary plasmacytoma is detected during screening, evaluation will be repeated during treatment to confirm a response of PR or better, or to confirm PD or as clinically indicated. Clinical assessment of measurable sites of extramedullary disease will be performed and evaluated locally every 28 ( $\pm$  7) days for subjects with a history of plasmacytoma or as clinically indicated during treatment for other subjects. If assessment can only be performed radiologically, then evaluation of extramedullary plasmacytomas may be done every 12 weeks. The

same technique, which may include clinical evaluation by palpation, ultrasound, CT scan, magnetic resonance imaging (MRI), or PET/CT should be employed for each measurement of plasmacytoma dimensions as clinically appropriate (refer to Section 12.11). Bidimensional lesion measurements must be performed and recorded in the designated eCRF.

#### **9.2.2.5      Progressive Disease Assessment**

Confirmation of PD requires 2 consecutive assessments made before the institution of any new therapy, as well as no known evidence of progressive or new bone lesions if radiographic studies were performed. Radiographic studies are not required to satisfy these response requirements. Bone marrow, plasmacytoma, and skeletal survey assessments are not required to be confirmed by repeat testing.

Local laboratory evaluation will not be accepted. The assessments outlined in Section 12.11 are required for PD. Subjects will be considered to have PD if they meet the criteria for progression by a variable that was not considered measurable at baseline; however, for subjects who had a measurable serum or urine M-spike at baseline, progression cannot be defined by increases in SFLC alone (Kumar et al, 2016).

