PD	

• Increase of 25% from lowest confirmed response value in 1 or more of the following:

– Serum M-component (absolute increase must be ≥ 0.5 g/dL if the lowest M-component was < 5 g/dL)

– Urine M-component (absolute increase must be ≥ 200 mg per 24 hours)

– Only in subjects without measurable serum and urine M protein levels: the difference between involved and uninvolved FLC levels (absolute increase must be > 10 mg/dL)

• Increase of serum M-component of ≥ 1 g/dL if the lowest M-component was ≥ 5 g/dL)

• Appearance of new lesion(s), ≥ 50% increase from nadir in SPD of > 1 lesion, or ≥ 50% increase in longest diameter of a previous lesion > 1 cm in short axis

• ≥ 50% increase in circulating plasma cells (minimum of 200 cells per µL) if this is the only measure of disease

CR = complete response; FC = flow cytometry; FLC = free light chain; PD = progressive disease;  
PR = partial response; sCR = stringent complete response; SFLC = serum-free light chain; SPD = maximal perpendicularly diameter; VGPR = very good partial response

a In this study, only immunohistochemistry is used for response assessment.

All response categories (complete response [CR], stringent complete response [sCR], very good partial response [VGPR], partial response [PR]) require 2 consecutive assessments before the initiation of any new therapy, as well as no known evidence of progressive or new bone lesions if radiographic studies were performed. Radiographic studies are not required to satisfy these response requirements. Bone marrow, plasmacytoma, and skeletal survey assessments are not required to be confirmed by repeat testing.

Subjects will continue in the last confirmed response category until there is confirmation of progression or improvement to a higher response status; subjects cannot move to a lower response category.

For sCR: presence/absence of clonal cells is based upon the kappa/lambda ( $\kappa/\lambda$ ) ratio. An abnormal kappa lambda ratio by immunohistochemistry and/or immunofluorescence requires a minimum of 100 plasma cells for analysis.

Response criteria for all categories and subcategories of response, except CR, sCR, and PD are applicable only to patients that have measurable disease, defined by at least 1 of:

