- Immunoglobulin (Ig) G multiple myeloma: serum monoclonal paraprotein (M-protein) level  $\geq 1.0$  g/dL,
- IgA, IgD, IgE multiple myeloma: serum M-protein level  $\geq 0.5$  g/dL,
- urine M-protein  $\geq 200$  mg/24 hours,
- in subjects without measurable serum or urine M-protein, serum-free light chain (SFLC)  $\geq 100$  mg/L (involved light chain) and an abnormal serum kappa lambda ratio

Determination of PD while on study requires 2 consecutive assessments (to confirm response or PD, 2 discrete samples are required; samples may be drawn on the same day) before classification of PD and/or the institution of new therapy. Confirmative samples for PD after new therapy can be used. Serum M-component increases of  $\geq 1$  g/dL from nadir are sufficient to define progression if nadir M-component is  $\geq 5$  g/dL.

Plasmacytomas: A plasmacytoma is considered measurable if the longest diameter is at least 1 cm and the product of the cross diameters is at least 1 cm^2. Progression is defined as appearance of a new lesion(s),  $\geq 50\%$  increase from nadir of the sum of the products of the maximal perpendicular diameter (SPD) of the measurable lesion as measured serially, or a  $\geq 50\%$  increase in the longest diameter of a previous lesion  $> 1$  cm short axis;  $\geq 50\%$  increase in plasma cells if this is the only measure of disease.

---

For defining nadir, in the case where a value is felt to be a spurious result per physician/Independent Review Committee (IRC) discretion (eg, a possible laboratory error), that value will not be considered when determining the lowest value.

Sources: Kumar et al, 2016; Rajkumar et al, 2011; Durie et al, 2006.

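### Two separate wording conflicts: the PD confirmation rule in Protocol 9.2.2.5 carries a bone-lesion clause that belongs to response, and Protocol 9.1.4 and SAP 3.1 stop survival follow-up at a therapy switch where Table 2-1 does not

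*Protocol*

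**What the plan says.** **Confirmation of PD.** Protocol 9.2.2.5 asks for two consecutive assessments "before the institution of any new therapy, as well as no known evidence of progressive or new bone lesions", where radiographic studies were done. Its next sentence still speaks of response requirements. Appendix 11 (Section 12.11) has nearly the same sentence, but there it is the response categories sCR, CR, VGPR and PR that "require 2 consecutive assessments before the initiation of any new therapy, as well as no known evidence of progressive or new bone lesions". Appendix 11 has its own PD confirmation rule. It carries no bone-lesion condition, specifies "to confirm response or PD, 2 discrete samples are required; samples may be drawn on the same day", and adds: "Confirmative samples for PD after new therapy can be used". Protocol 9.2.2 cites 9.2.2.5 for the confirmed PD that ends disease assessments.

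**Bone lesions elsewhere.** For response confirmation, Protocol 9.2.2.1 states: "all categories also require no known evidence of progression including new bone lesions if radiographic studies were performed". Protocol 9.2.2.3 has bone imaging repeated when worsening symptoms point to PD.

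**Survival follow-up.** Protocol 9.1.4 and SAP 3.1 give two tracks. Subjects with confirmed PD before month 12 are followed for survival to month 12. Subjects without confirmed PD are followed for survival, response and new treatment, and all of that ends at the first subsequent antimyeloma treatment. The Survival row of Protocol Table 2-1 follows every subject who stops treatment before 12 complete cycles to month 12, with no stop at new therapy and no condition on confirmed PD. The row beneath it, for subsequent therapies, does carry that stop. The last sentence of 9.1.4 refers collection of survival information to Table 2-1.

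**The concern.** In the first conflict, the PD rule contains a condition that works against it: a finding that signals progression elsewhere in the protocol becomes, in 9.2.2.5, a reason not to confirm it. An investigator who applies that section word for word and one who applies Appendix 11 can classify the same subject differently. This touches the investigator-based sensitivity analyses of PFS, TTP and DOR, the concordance summaries, the confirmed-progression cut-off in the SAP's definition of investigator best overall response, and the moment at which assessments stop.

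In the second, sites have inconsistent instructions on whether to keep contacting a subject who changes therapy without confirmed PD. OS is a secondary endpoint with Kaplan-Meier rates at 6 and 12 months and a stratified hazard ratio planned (SAP 9.5.2). A switch of therapy is unlikely to be unrelated to prognosis, so ending contact there may make the censoring informative.

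**Working it through.** The plan gives no figure to reproduce. The check sets the rules side by side and runs assumed cases through them. Days are counted from randomization, and times use the SAP formula (date − randomization date + 1) / 30.4.

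**1. PD rule.** Take a subject in PR with an M-protein rise shown on two samples on day 168 (same-day samples are allowed by Appendix 11) and a new bone lesion on imaging.

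- Appendix 11: PD is confirmed. PFS time = (168 + 1) / 30.4 = 5.6 months.
- 9.2.2.5, read literally: the lesion is known evidence of a new bone lesion, so PD is not confirmed. Appendix 11 then says: "Subjects will continue in the last confirmed response category until there is confirmation of progression or improvement to a higher response status". The subject stays in PR and assessments go on.
- 9.2.2.1: the same lesion is evidence of progression and would block confirmation of any response.

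The last line also limits the effect on investigator best overall response. Even if the progression cut-off is not triggered, a later, better response would fail the response rule.

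**2. Confirmation timing.** 9.2.2.5 wants both assessments before new therapy, while Appendix 11 also accepts confirmatory samples taken afterwards. The two differ only for a subject with no second sample before the switch. Same-day samples are allowed and scheduled assessments end at the switch, so this has little reach and is only something to tidy in the same edit.

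**3. Survival follow-up.** Assume last dose on day 84, new therapy on day 91, no confirmed PD, and the subject alive throughout.

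- Safety follow-up: 84 + 30 = day 114.
- Text of 9.1.4 and SAP 3.1: follow-up ended at the switch on day 91, so there are 0 survival contacts after the safety visit. Last known alive = (114 + 1) / 30.4 = 3.8 months, unless another source gives a later date.
- Survival row: the first contact is 28 days after the safety visit (day 142), then every 28 days up to day 365. That gives days 142, 170, 198, 226, 254, 282, 310 and 338, which is 8 contacts. Last known alive = (338 + 1) / 30.4 = 11.2 months.
- Difference: 338 − 114 = 224 days, and 224 / 30.4 = 7.4 months.
- Same dates with confirmed PD: 9.1.4 itself gives the 8 contacts.

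The bone-lesion clause plays no part in this case. Any switch without confirmed PD produces it.

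**The case against.** **Section 12.11 still governs PD.** 9.2.2.1 holds disease response and progression to Section 12.11. 9.2.2.5 itself requires the Section 12.11 assessments for PD and says skeletal survey findings need no repeat test. SAP 3.1 puts investigator and IRC under the same IMWG criteria. A sensible investigator would treat the clause as a copying slip. This stands, and it limits the consequence to possible inconsistency. It does not remove the clause, and 9.2.2 points to 9.2.2.5 for confirmed PD.

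**The new-lesion criterion is weak support.** The PD list in Appendix 11 includes appearance of new lesions, but the same appendix develops that item under plasmacytomas. This stands. The conflict rests on 9.2.2.1, on 9.2.2.3, and on the absence of any bone-lesion condition in Appendix 11's own PD confirmation rule.

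**9.1.4 defers to Table 2-1.** Its closing sentence sends survival collection to the schedule, and Protocol Section 9 calls adherence to the schedule essential. On that reading the 8 contacts take place. This stands too: zero contacts is one reading, not the only one. But the stop at new therapy is written out in both 9.1.4 and SAP 3.1, and in Protocol 5.1 the sentence on subjects without confirmed PD does not mention survival at all. A site could reasonably stop.

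**Other sources of dates.** The SAP takes last known alive from relevant CRFs and vendor data. That limits the loss but does not replace scheduled contacts.

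**Conclusion.** Both inconsistencies are real, and each is minor to moderate. They should be treated as separate points.

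A reader might infer that the copied clause distorts the gated PFS test. The documents do not support that: primary PFS uses IRC assessment under Section 12.11, whose PD confirmation rule has no such clause. A reader might also infer that the clause decides who is followed for survival. Confirmed status does select the track in 9.1.4, but for the clause to matter a subject would need progressive or new bone lesions, a literal reading against Section 12.11, a switch of therapy, and a site that sets Table 2-1 aside. The survival conflict needs none of the first two and stands alone.

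The first point is therefore a risk of inconsistent investigator-assessed PD and of an unclear end to assessments. The second is a risk of early, possibly informative OS censoring, illustrated by 3.8 against 11.2 months for one subject on assumed dates and on one reading of 9.1.4. OS is outside the testing hierarchy. The documents do not say how many subjects would be affected, and no directional bias or loss of power is claimed.

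**What to change.** - **Protocol 9.2.2.5:** delete the bone-lesion condition from the PD rule, and the leftover reference to response requirements with it. In the same edit, make its confirmation-timing sentence agree with Appendix 11 so that the protocol states one rule.
- **Protocol 9.1.4 and SAP 3.1:** align both with the Survival row of Table 2-1, so that survival is followed to 12 months after randomization whether or not new therapy has started. The stop at new therapy can remain for disease response assessments and reporting of new treatment.

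The cost is amendment wording, including submission of the protocol amendment to the IRB/IEC, plus survival contacts that Table 2-1 already lists. No sample or procedure is added, and neither the sample size nor any test changes.
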